## 7. STATISTICAL CONSIDERATIONS

### 7.1. Power calculations

We will enroll 700 participants. Participants will be randomized to one of 2 interventions (fenofibrate plus usual care vs. placebo plus usual care). Assuming feasible distributions of participants across each of the five hierarchies from the available published evidence, we performed 10,000 simulations of rank distributions of 700 participants, and determined that there will be 80% power at an alpha of 0.0492 (allowing for one interim analysis at 50% of enrollment with an alpha of 0.0054) to observe an 11% difference in median rank scores between the treatment arms. Power calculations were performed using python and PASS16.

Enrollment of 700 participants will increase our power for secondary outcomes. For the secondary outcome of number of days alive, out of the intensive care unit, free of mechanical ventilation (invasive and non-invasive), extracorporeal membrane oxygenation (ECMO) or maximal available respiratory support in the 30 days following randomization, assuming a standard deviation of 7 (the SD from the REPLACE COVID trial for this outcome), a sample size of 700 would have 90% power to estimate a 1.7 day mean difference between treatment arms. Assuming that the SD may be higher in the current study with the inclusion of outpatients, we would have a sufficient power to estimate a 3.4 day mean difference between treatment arms with a SD of 14.

For the secondary outcome of the WHO ordinal scale, based on the ordinal scale distributions from the Remdesivir trial, we would have 90% power to observe an OR of 1.5 for clinical improvement in the ordinal scale. Given the expected lower severity of illness in our participants, with an adjusted reasonable distribution towards the lower end of the scale, we would have 90% power to observe an OR of 1.7.

For the exploratory outcome of all-cause death, assuming a death rate of 14% (observed in REPLACE COVID), we would have sufficient statistical power to detect a HR of 1.4. Considering the mixed inclusion of inpatients and outpatients, if the death rate is 5%, we would have sufficient statistical power to detect a HR of 1.7.

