### 7.2. Data Analysis Plan

The sample, both the baseline characteristics and the outcomes, will be explored and described using graphical techniques and summary statistics (means, medians, proportions and measures of variability) as appropriate. The initial description will consider the sample as a whole as well as by treatment arm.

The primary outcome variable will be the global rank score, as used previously in several similar randomized controlled trials to facilitate evaluation of composite outcomes of binary and continuous findings accounting for censorship for death. The predictor of interest for all outcomes will be randomized intervention (fenofibrate vs. control), with analyses based upon the total number of randomized participants. Initial descriptive estimates of all measures will be generated for study participants by treatment group. Statistics will include estimates of central tendency, measures of variability, and derived moments of skewness and kurtosis. Analyses of distributional properties will be performed to determine if variance stabilizing or normalizing transformations should be applied. Outliers will be assessed via visual inspection of distributions and checked for accuracy. Additionally, the intervention groups will be compared using Fisher's Exact tests.

The primary and secondary outcomes will be analyzed using a two-sided Wilcoxon rank sum test. Estimation, and 95% confidence intervals, of the differences between arms will be based on the Hodges-Lehman median difference as well as the Mann-Whitney Parameter, the probability that a subject from the fenofibrate arm has a score greater or equal to that of a subject for the control. This will be followed by a more comprehensive linear regression analysis allowing for assessments of the treatment effect on each continuous outcome of interest while controlling for effects of covariates including age, sex, inpatient vs. outpatient status at enrollment,  $\text{FiO}_2/\text{SpO}_2$  at the time of enrollment, ethnicity, body mass index, altitude above sea level and history of diabetes at baseline.

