### Secondary Endpoints (Pre-specified in the protocol)

Secondary endpoints pre-specified in the protocol are:

- (1) Number of days alive, out of the intensive care unit, free of mechanical ventilation (invasive and non-invasive), extracorporeal membrane oxygenation (ECMO) or maximal available respiratory support in the 30 days following randomization.
- (2) A seven-category ordinal scale consisting of the following categories: 1, not hospitalized with resumption of normal activities; 2, not hospitalized, but unable to resume normal activities; 3, hospitalized, not requiring supplemental oxygen; 4, hospitalized, requiring supplemental oxygen; 5, hospitalized, requiring nasal high-flow oxygen therapy, noninvasive mechanical ventilation, or both; 6, hospitalized, requiring extracorporeal membrane oxygenation (ECMO), invasive mechanical ventilation, or both; and 7, death.
- (3) A global rank score similar to the primary endpoint, but using a more comprehensive COVID-19 symptom scale instead of the dyspnea Borg scale (Appendix 1 of Protocol).

**Exploratory endpoints** will include:

- (1) Time to all-cause death.
- (2) Time to hospitalization among subjects initially randomized as outpatients
- (3) Time to discharge among subjects initially randomized as inpatients
- (4) Number of days alive and out of the hospital during the 30 days following randomization.
- (5) A global rank score similar to the primary endpoint, but built only with factors 1-4

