### Descriptive Statistics (Intention to treat cohort)

Analyses will be for the overall cohort, stratified by arm and stratified by in/out patient status at randomization. The outcomes and baseline characteristics of the subjects will be described using proportions for categorical variables and means/medians as well as standard deviations (SD) and interquartile range (IQR) for continuous variables.

**Primary Analysis:** This analysis will use a two-sided van Elteren test, the stratified version of the Wilcoxon rank sum test. For each stratum, estimation, and 95% confidence intervals of differences between arms will use both the Hodges-Lehman median difference and the Mann-Whitney Parameter, the probability that a subject from the treatment arm has a score greater or equal to that of a subject for the control. In addition to the primary outcome, the Wilcoxon test will be used to test hypotheses involving the continuous secondary and exploratory outcomes.

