### Secondary Analysis:

**Time-to-event outcomes.** Kaplan-Meier curves and cumulative event plots will be used to graphically explore differences between arms. The Cox model will be used to assess differences by arm in the risk of all-cause death and the risk of hospitalization for subjects who were outpatient at the time of randomization. Subjects who withdrew from the study will be considered censored. The proportional hazards assumption will be assessed, and violations addressed using a time by intervention term or a parametric model. Time to discharge from hospital will be modelled using a competing risk model with death as the competing risk.

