### Regression models

Linear regression analysis to estimate the treatment effect for each continuous outcome of interest will adjust for covariates including age, sex, inpatient vs. outpatient status at enrollment, FiO2/SpO2 at the time of enrollment, ethnicity, body mass index, altitude above sea level and history of diabetes at baseline. Although not specified in the initial protocol, at the recommendation of the DSMB, we will add Country as a fixed effect with the goal of adjusting for a broad indicator of treatment practices, timing of variants, and timing of surges. We will also perform sensitivity analyses clustered study site.

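### The SAP does not name a test or effect estimate for the seven-category ordinal secondary endpoint; the protocol's fallback needs three cheap corrections, including the odds ratio on which power was stated

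*SAP*

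**What the plan says.** The SAP lists secondary endpoint 2 as "A seven-category ordinal scale consisting of the following categories", running from 1 (not hospitalised, normal activities resumed) to 7 (death). A higher score is therefore a worse outcome.

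- **SAP, Primary Analysis paragraph.** The primary endpoint gets a van Elteren test. Estimation within each stratum "will use both the Hodges-Lehman median difference and the Mann-Whitney Parameter". The only sentence on testing other outcomes is that "the Wilcoxon test will be used to test hypotheses involving the continuous secondary and exploratory outcomes".
- **SAP, Regression models.** "Linear regression analysis to estimate the treatment effect for each continuous outcome of interest" is planned, with covariates. No ordinal or logistic model appears.
- **SAP, Secondary Analysis.** Time-to-event outcomes have their own methods: "The Cox model will be used to assess differences by arm in the risk of all-cause death", the same model is used for hospitalisation, and a competing-risk model for discharge.
- **SAP, Descriptive Statistics.** Outcomes and baseline characteristics are "described using proportions for categorical variables".
- **Protocol 7.2.** "The primary and secondary outcomes will be analyzed using a two-sided Wilcoxon rank sum test". Estimates with 95% confidence intervals are the Hodges-Lehmann difference and the Mann-Whitney parameter. The latter is defined as the chance that a fenofibrate score is at least as high as a control score.
- **Protocol 7.1.** The ordinal endpoint is powered on an odds ratio: 90% power for 1.5 and, for the lower-severity distribution expected in this trial, "we would have 90% power to observe an OR of 1.7".

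The SAP's opening paragraph says that it follows the protocol's analysis plan and adds detail.

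**The concern.** The protocol's wording covers all secondary outcomes. The SAP's covers only the continuous ones, and an ordinal scale with seven levels is not obviously among them. An analyst working from the SAP has no stated test or effect measure for endpoint 2 and must go back to the protocol.

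The protocol's package suits this endpoint poorly in three ways. The Hodges-Lehmann difference is the median of all between-arm pairwise differences, so heavy ties pull it to 0. The Mann-Whitney parameter, as worded, counts each tie in full, so its no-effect value is not 0.5. And the effect was planned as an odds ratio, but no analysis estimates one. The report could show a small p-value beside a difference of 0 and a probability that cannot be read without knowing the tie rate, with nothing to set against the planned 1.5 or 1.7.

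**Working it through.** **Inputs.** From the documents: N = 700, 1:1, so 350 per arm; odds ratios 1.5 and 1.7; 90% power. Assumed: two-sided alpha 0.05 (no alpha is stated for this endpoint), proportional odds, and three control-arm mixes over categories 1 to 7, since the documents give none:

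- mild: .55/.20/.05/.08/.05/.04/.03
- moderate: .35/.25/.06/.10/.07/.07/.10
- severe: .20/.25/.10/.15/.10/.10/.10

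**Step 1: the plan's own figure.** The proportional-odds sample-size formula is N = 12(z₁+z₂)² / [ln(OR)² × (1 − Σp̄³)], with p̄ the category proportions averaged over arms.

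- OR 1.5: even with no ties (Σp̄³ = 0), N = 12 × (1.960 + 1.282)² / 0.4055² ≈ 767. With 700, power is at most 87.2%.
- The odds ratio detectable with 90% power is at best exp(√(126.1/700)) = 1.53, which prints as 1.5 to one decimal.
- OR 1.7: 90% power needs Σp̄³ = 1 − 126.1/(700 × 0.5306²) = 0.36, a strongly low-end mix.

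Both figures fit a proportional-odds calculation after rounding. This is not a power error.

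**Step 2: Hodges-Lehmann difference.** It is 0 whenever neither direction takes more than half of the pairs. At OR 1.7 the chance that a fenofibrate patient does strictly better than a control patient is 0.361, 0.455 and 0.495 in the three mixes. All are below one half, so the population value is 0 in each. Simulated shares of trials (4,000 per cell):

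| Mix | Estimate = 0, OR 1.5 | Estimate = 0, OR 1.7 | 95% CI = 0 to 0, OR 1.7 | Wilcoxon power, OR 1.7 |
|---|---|---|---|---|
| mild | 100% | 100% | 100% | 95% |
| moderate | about 99.5% | 98% | about 55% | 97% |
| severe | about 85% | about 60% | about 4-5% | 98% |

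Repeat runs of the severe mix at OR 1.7 ranged from 59% to 64%. With even flatter assumed mixes the share at OR 1.7 falls to 42% (spread) and 26% (uniform).

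**Step 3: Mann-Whitney parameter.** The probability of a tie under no effect is Σp²: 0.356, 0.218 and 0.165. As worded, the no-effect value is 0.5 + Σp²/2:

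| Mix | No-effect value, as worded | At beneficial OR 1.7, as worded | At OR 1.7, ties as half |
|---|---|---|---|
| mild | 0.678 | 1 − 0.361 = 0.639 | 0.433 |
| moderate | 0.609 | 1 − 0.455 = 0.545 | 0.420 |
| severe | 0.583 | 1 − 0.495 = 0.505 | 0.416 |

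Read as worded against 0.5, a real benefit in the mild mix gives 0.64, on the wrong side of 0.5. With ties as half, the parameter is 0.42 to 0.43 against 0.5; turned round so that higher favours fenofibrate, it is 0.567, 0.580 and 0.584. So it does register the effect.

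**Step 4: what an odds ratio would add.** The standard error of the log odds ratio is about √(12/[700 × (1 − Σp̄³)]).

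- Mild mix, OR 1.7 (Σp̄³ = 0.236): SE 0.150, 95% CI about 1.27 to 2.28.
- Severe mix, OR 1.5 (Σp̄³ = 0.037): SE 0.133, 95% CI about 1.15 to 1.95.

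**Step 5: stratifying the rank test.** Assume half the patients are outpatients with the mild mix and half inpatients with the severe mix, with OR 1.5 in each. Unstratified Wilcoxon power is about 77%, van Elteren about 82% (8,000 trials). Another assumed mix gave about 70% and 76%. The gain depends on how far the two groups differ.

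**The case against.** The strongest reply is that nothing is missing. The SAP says it follows the protocol and lists the ordinal scale as pre-specified there. The protocol gives every secondary outcome a two-sided Wilcoxon test and two estimators with confidence intervals, and nothing in the SAP withdraws this. The Wilcoxon test is the score test of the proportional-odds model without covariates, so planning and testing agree. An effect size used for power need not be the one reported.

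Most of that stands, and it rules out several stronger readings.

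- A reader might infer that the SAP analyses continuous outcomes only. It does not: it has Cox and competing-risk models, and proportions for categorical variables.
- A reader might infer that the endpoint has no valid test or no usable effect estimate. The protocol supplies both; with ties as half, the Mann-Whitney parameter is a sound ordinal effect measure.
- A reader might infer that a Hodges-Lehmann difference on seven categories is always 0. That depends on the mix, and Step 2 shows mixes where it often is not.

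It can also be said that the authors surely mean ties as half, since the reference they cite is titled as giving intervals compatible with the Wilcoxon test. That is likely, but both documents word the definition otherwise. On a scale where 16-36% of pairs tie under no effect, the difference is too large to leave to the programmer.

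**Conclusion.** The point holds as a cheap improvement to a secondary endpoint, not as a failure of the analysis. The SAP's wording is narrower than the protocol's and leaves endpoint 2 unnamed. In the low-severity population that Protocol 7.1 expects, the Hodges-Lehmann difference will almost certainly be 0 whether or not the drug works. The Mann-Whitney parameter is informative only once ties and direction are settled. No planned analysis returns the odds ratio on which power was stated.

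The textual findings rest on the documents alone. The sizes rest on assumed category mixes, proportional odds and 350 analysed per arm. That Hodges-Lehmann is uninformative is firm for mild and moderate mixes and weaker for severe ones. The primary endpoint and its test are not touched.

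**What to change.** Add one paragraph to the SAP, before unblinding, that names secondary endpoint 2 and does the following:

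1. Keeps the rank test, stratified by inpatient/outpatient status at randomisation.
2. Adds a proportional-odds model of category on treatment and inpatient/outpatient status. The other randomisation factors (site, sex, age group) may be added. It reports the common odds ratio with its 95% CI, oriented so that values above 1 favour fenofibrate, and a check of the proportional-odds assumption.
3. Keeps the Mann-Whitney parameter with its 95% CI, with ties counted as half, a no-effect value of 0.5 and the direction stated.
4. Drops the Hodges-Lehmann difference for this endpoint only.

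The cost is a paragraph and a standard model fit; no new data are needed. The downside is reliance on proportional odds. It can be checked, and the rank test stands beside the model if the check fails.

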### Secondary Analysis:

**Time-to-event outcomes.** Kaplan-Meier curves and cumulative event plots will be used to graphically explore differences between arms. The Cox model will be used to assess differences by arm in the risk of all-cause death and the risk of hospitalization for subjects who were outpatient at the time of randomization. Subjects who withdrew from the study will be considered censored. The proportional hazards assumption will be assessed, and violations addressed using a time by intervention term or a parametric model. Time to discharge from hospital will be modelled using a competing risk model with death as the competing risk.

### Regression models

Linear regression analysis to estimate the treatment effect for each continuous outcome of interest will adjust for covariates including age, sex, inpatient vs. outpatient status at enrollment, FiO2/SpO2 at the time of enrollment, ethnicity, body mass index, altitude above sea level and history of diabetes at baseline. Although not specified in the initial protocol, at the recommendation of the DSMB, we will add Country as a fixed effect with the goal of adjusting for a broad indicator of treatment practices, timing of variants, and timing of surges. We will also perform sensitivity analyses clustered study site.

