#### Inclusion Criteria

- (1) Age 18 years or older
- (2) A diagnosis of COVID-19, based on: (a) A compatible clinical presentation with a positive laboratory test for SARS-CoV-2, or (b) Considered by the primary team to be a Person Under Investigation undergoing testing for COVID-19 with a high clinical probability, in addition to

- compatible pulmonary infiltrates on chest x-ray (bilateral, interstitial or ground glass opacities) or chest CT.
- (3) Able to provide informed consent.
- (4) Fewer than 14 days since symptom onset.

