### FEnofibRate as a Metabolic INtervention for Coronavirus Disease 2019 (COVID-19): A randomized controlled trial (FERMIN trial)

April 6, 2022

This document details the statistical analysis plan in detail, including analyses that were pre-specified prior to data locking and unblinding. The document follows the original protocol analysis plan, but includes more methodologic detail and additional pre-specified analyses that are based on data not available at the time the protocol was written. These include: (1) A stratified analysis according to the specific fenofibrate/fenofibric acid preparation used, given recent data suggesting that there may be differential potency of fenofibrate as opposed to fenofibric acid *in vitro*, at least in some viral strains and/or culture systems; (2) Stratified analysis suggested by the trial DSMB during the course of the study, such as according to country, baseline disease severity, and COVID-19 pandemic epochs in which specific strains predominated.

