### Subgroup analyses

Exploratory subgroup analyses will follow the plans described above with emphasis on estimation and confidence intervals for the purpose of hypothesis generation in future studies. Subgroups include

1. Sex
2. Age (categorized by < or  $\geq$  the median value in the study population),
3. Race
4. Diagnosis of diabetes at randomization,
5. Body mass index (categorized by obese or non-obese)
6. Inpatient vs. outpatient status at the time of enrollment,
7.  $\text{FiO}_2/\text{SpO}_2$  at the time of enrollment (categorized by < or  $\geq$  the median value in the study population)
8. Duration of symptoms prior to randomization (<7d vs.  $\geq$ 7 days) and
9. Fasting triglyceride levels (when available, categorized by < or  $\geq$  the standard median value).
10. Country
11. Baseline disease severity (low, medium, high based on WHO criteria) \*
12. Enrollment epoch/period (will divide into 3 epochs, early, mid, late)
13. Fenofibrate formulation (fenofibrate nanoparticle formulation (used in the USA, Lebanon and Greece), fenofibrate micronized formulation (used in Peru and Mexico) or fenofibric acid (used in Colombia). We will also do a stratified analysis of all fenofibrate formulations vs. fenofibric acid. Although all preparations utilized are approximately dose-equivalent, these analyses are pre-specified due to potential pharmacokinetic differences between the formulations, as well as recent data suggesting that there may be differential potency of fenofibrate as opposed to fenofibric acid *in vitro*, at least in some viral strains and/or culture systems. We note, however, that potential *in vitro* differences between fenofibrate and fenofibric acid are likely much less relevant *in vivo*, since fenofibric acid is the active metabolite of fenofibrate.

Country, Baseline Disease Severity, and Enrollment epoch/period were recommended as subgroups by our DSMB and prior to conclusion of enrollment. Their recommendation acknowledged variation in standard of care among different countries as well as subgroups that

were pre-defined prior to initiation of the study. Fenofibrate formulation was also added as a subgroup analysis due to the use of 3 different formulations depending on availability within a given country. We will also visually explore trends of epoch by country, plotting study month at enrollment versus summary statistics of the primary outcome by treatment and country.

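### The Country term in the SAP's adjusted regression cannot capture within-country timing of variants and surges, and days since symptom onset is not a named covariate; the cost is some precision in a secondary analysis

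*SAP*

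**What the plan says.** The SAP (Regression models) plans a linear regression for each continuous outcome. It "will adjust for covariates including age, sex, inpatient vs. outpatient status at enrollment", then baseline FiO2/SpO2, then "ethnicity, body mass index, altitude above sea level and history of diabetes at baseline". Protocol section 7.2 names the same covariates. On the DSMB's recommendation the SAP adds Country as a fixed effect, with the goal of "adjusting for a broad indicator of treatment practices, timing of variants, and timing of surges". Neither document names enrolment date, month or period, or time since symptom onset, as a covariate.

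Both variables appear elsewhere. SAP, Subgroup analyses, lists "Enrollment epoch/period (will divide into 3 epochs, early, mid, late" as item 12 and "Duration of symptoms prior to randomization", cut at 7 days, as item 8. These are exploratory. The same section plans a descriptive plot of the primary outcome by study month, arm and country. Protocol section 2.3, inclusion criterion 4, admits patients with "Fewer than 14 days since symptom onset", that is, 0 to 13 completed days.

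The regression is not the primary analysis, which is a van Elteren test. Linear regression returns once more in the SAP, with multiple imputation, as the sensitivity analysis of the primary outcome if missingness exceeds 5% (Sensitivity Analyses, item 3).

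**The concern.** Variants and surges are events in calendar time. They arrive and pass within a country while the trial is enrolling there. A fixed effect is one number per country for the whole trial, so it can carry only the part of calendar time that differs on average between countries. The model therefore does only part of what the SAP gives as the reason for adding the term.

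Time since onset is a second time axis. Two participants randomised on the same day in the same country can be almost two weeks apart in their illness. The SAP considers this worth a subgroup but leaves it out of the named covariates.

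At stake is the precision of the adjusted treatment effect, and whether a reader is right to believe that the adjusted model has dealt with pandemic timing.

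**Working it through.** **1. The plan's own figure.** The protocol's nearest power statement for a continuous outcome is in section 7.1: N = 700 (1:1, so 350 per arm), SD 7, difference 1.7 days, 90% power. With two-sided alpha 0.05 (not stated for this figure):

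- SE = 7 × √(2/350) = 0.529
- 1.7/0.529 = 3.213, and 3.213 − 1.960 = 1.253, so power = 89.5%
- Total N for 90% power = 714

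At alpha 0.0492 the results are 89.4% and 716. The stated figure reproduces.

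**2. Effect of adding the two time terms.** Let R² be the share of the variance left by the listed covariates that enrolment period and days since onset explain. The documents give no value, so a range is assumed. The SE is multiplied by √(1 − R²), and the equivalent N is 700/(1 − R²). The SD of 7 is treated as the SD before the time terms enter. If the listed covariates already reduce it, power starts higher and fewer points are left to gain.

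| Assumed R² | Residual SD | SE reduction | Equivalent N | Power for 1.7 days | Difference detectable at 90% |
|---|---|---|---|---|---|
| 0 | 7.000 | 0 | 700 | 89.5% | 1.715 |
| 1% | 6.965 | 0.5% | 707 | 89.8% | 1.707 |
| 2% | 6.930 | 1.0% | 714 | 90.1% | 1.698 |
| 5% | 6.823 | 2.5% | 737 | 90.9% | 1.672 |
| 10% | 6.641 | 5.1% | 778 | 92.3% | 1.627 |

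These figures are before the cost in degrees of freedom.

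**3. Degrees of freedom.** Three epochs as main effects plus a linear onset term use 2 + 1 = 3 degrees of freedom, and 3/700 is about 0.4% of variance. The SAP names six countries (Subgroup analyses, item 13). Full country-by-period has 6 × 3 = 18 cells. Country already accounts for 6 of them, so the period terms use 12 degrees of freedom; 12/700 = 1.7%, or about 2%. That would cancel the gain if R² were near 2%.

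**4. How much calendar time Country absorbs, and whether omission biases.** A simulation used 700 participants in six countries, permuted blocks of 4 within country, an assumed 20-month enrolment, three epochs, an assumed 5% of variance for each time axis, a true effect of 1.7, and 1,500 runs per setting.

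- The share of epoch variance absorbed by Country was 0.7% when all countries enrol over the same window, 1.8% with slight stagger, 12% with moderate stagger and 60% with strong stagger.
- Mean estimates lay between 1.685 and 1.707 in every model, so there was no bias.
- With fully overlapping windows, adding epoch and days since onset cut the mean model SE from 0.529 to 0.502. Power rose from 0.899 to 0.921.
- With those windows, adding epoch alone left the actual spread of the estimates unchanged (0.510 and 0.511) while the reported SE fell from 0.529 to 0.516. Blocking in time order had already balanced the arms over calendar time, so the calendar term mainly brings the reported SE into line with the true one. The trial's strata are finer than those simulated, so its balance over time will be looser.

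**The case against.** The strongest reply is that the SAP presents Country as a broad indicator. That is the language of a coarse proxy, not a claim to remove within-country change. The regression is secondary, and leaving a prognostic covariate out of it is a choice about precision, not an error. The covariate list is also introduced as non-exhaustive. Most of this stands, and it limits the point to an improvement plus a clarification. It does not remove the mismatch between the stated aim and the model, and an open list is itself a reason to name the terms.

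A reader might infer more than the documents support:

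- **That both time axes remain wholly in the error term.** Country removes the between-country part of calendar time. How large that part is depends on how staggered enrolment was. Protocol section 2.4 describes competitive enrolment across active sites, while the version history shows countries joining later; the extent is not given. Baseline FiO2/SpO2 and inpatient status may also carry some of the effect of symptom duration.
- **That the treatment effect is biased or the primary result weakened.** Randomisation is in permuted blocks stratified by site (protocol section 2.6), and the primary test does not use this regression.
- **That the epoch subgroup mixes strains and so cannot show a strain effect.** The SAP introduction describes epochs as "COVID-19 pandemic epochs in which specific strains predominated". The subgroup list gives early, mid and late without cut-points and does not say that one split serves all countries. No variant dates appear in the documents. The two statements can be read together, so strain mixing is conjecture.
- **That the gain is large.** Nothing in the documents shows how prognostic either variable is. A figure such as 20% of variance has no anchor.

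**Conclusion.** The point holds as a modest, low-cost improvement. A country constant adjusts only for average between-country differences, so part of the SAP's stated aim is not met, and days since onset is missing from the named covariates although the SAP uses it elsewhere. The effect is confined to the precision of the secondary adjusted regression and of any linear-regression sensitivity analysis. Under the assumed R² of 1% to 10%, the standard error would fall by about 0.5% to 5%, and power for the 1.7-day difference would rise by 0.3 to 2.8 percentage points. These sizes rest on that assumption and on the protocol's SD of 7. That Country cannot carry within-country change rests on neither.

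**What to change.** In SAP, Regression models:

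1. Add enrolment period as a prespecified covariate, either the three epochs with their cut-points stated or a smooth calendar-time term.
2. Add days since symptom onset as a continuous covariate.
3. Keep country-by-period for a sensitivity analysis, because its 12 degrees of freedom could cost as much as it gains.
4. State that Country alone adjusts only for average differences between countries.
5. Make the covariate list closed, and use the same list in the multiple-imputation regression.

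The cost is a few lines of text and about three degrees of freedom. Enrolment timing and symptom duration are already needed for the subgroups, so no new data collection is expected. The change should be dated before unblinding.
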